Telephone calls between baseline and 3 month on-site visits: The subjects/LAR will be contacted by study staff approximately every 15 days to assess progress, symptoms and dosing compliance. If it appears subject is experiencing adverse changes and the Investigator feels an on-site visit is warranted, the subject will be asked to come in for an interim clinic visit.

Visit 2: Week 12 (+/- 1 week)

At Visit 2, the participant will undergo a physical exam and FARS scoring. Medical history, changes to concurrent medications, adverse event diary and dosing will be reviewed and additional diaries dispensed, as needed. A physical examination will be conducted. Dosing of (+)- EPI will be adjusted depending on the performance of the 8m timed walk completed through the FARS assessment and/or cardiac assessment via MRI. If the participant shows improvement (as defined in section 3.1) compared to baseline in composite score, including the 8m timed walk or cardiac function by MRI, the medication dosage will remain the same. If the participant shows no improvement or worsening compared to baseline, the (+)- EPI dose will be increased. Additional investigations include:

- Physical Examination, Vitals, Blood Pressure
- Drug level analysis of (+)- EPI in blood
- FARS Assessment
- Blood chemistry
 - Serum BNP, calcium, cardiac troponin I, CBC, ceruloplasmin, creatinine with eGFR, frataxin, , hemoglobin A1C, iron, mitochondrial complex I-V, potassium, PT/PTT, sodium, and ST2, triglycerides, and liver panel (ALT, AST, and Alkaline Phosphatase)
- Cardiac MRI with BOLD
- Urine pregnancy test

Telephone calls between 3 month and 6 month on-site visits: The subjects/LAR will be contacted by study staff approximately every 15 days to assess progress, symptoms and dosing compliance. If it appears subject is experiencing adverse changes and the Investigator feels an on-site visit is warranted, the subject will be asked to come in for an interim clinic visit.

Visit 3: Final Evaluation- Week 24 (+/- 1 week)

At the final visit, the participant will undergo a physical exam and neurological/cardiac assessments. Changes in symptoms and any concurrent medications will be assessed and the dosing/adverse event diary will be reviewed and collected/retained. Final investigations include:

- Physical Examination, Vitals, Blood Pressure FARS Assessment
- Urine analysis: F2-isoprostane
- Blood sample(s)
 - Analysis of (+)- EPI drug level and follistatin/myostatin levels

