3.1 General Design

This is an open label, single center, and prospective phase II drug trial to assess the safety and efficacy of (+)-EPI in the treatment of Friedreich's ataxia. Duration of the trial including recruitment and final assessment is estimated at approximately 2 years: start date early 2016 to approximately late 2017, depending upon recruitment rate. Subjects will be evaluated at outpatient clinic visit appointments and interested qualified subjects will be consented and offered participation in this trial. Once consent has been obtained, baseline values will be established and subjects will begin treatment and follow-up over a 24 week period. Clinical and biochemical parameters shown in Table 1 will be assessed in each patient at baseline and at 3, 12 and 24 weeks after initiation of treatment. See Protocol Schedule of Events in Attachment II.

Subjects will be dispensed bottles of 25mg capsules of open-label (+) EPI with instructions for oral TID dosing to be taken on an outpatient basis. All subjects will start at 75 mg total daily dose. Those subjects showing improvement at 12 weeks as defined below, will continue at the starting dose level of 75 mg total daily dose (one, 25mg cap TID) to 24 weeks. Subjects showing no improvement or worsening at 12 weeks will have their dose escalated as described below for the remainder of the study, as tolerated.

Dose Escalation at 12 weeks: Those subjects showing no improvement or worsening in the 8 meter timed walk/FARS composite score or with no improvement in cardiac function by MRI at the 12-week clinical assessment, as compared to baseline, will have their dose increased at the 12 week visit to 150 mg total daily dose (two, 25mg caps TID) until 24 weeks, as tolerated.

Neurological Status Improvement Definition: If there is no change or the timed walk is longer at 12 weeks than at the baseline walk time or the FARs composite score has not changed or has

increased, as compared to baseline FARS composite score, this will be considered no improvement/worsening of neurological status. Improvement is defined as a greater than 1 point decrease in the FARS composite score, as compared to the baseline composite score [36].

Cardiac Status Improvement Definition: If the cardiac function is the same as baseline or worse at 12 weeks, this will be considered no improvement /worsening of cardiac LV structure/function.

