Attachment I
Friedreich's Ataxia Rating Scale

**NINDS CDE Notice of Copyright
Friedreich Ataxia Rating Scale (FARS)**

Availability:	The instrument is freely available here: http://www.ataxia-study-group.net/html/about/ataxiascales/fars
Classification:	Core
Short Description of Instrument:	
The Friedreich Ataxia Rating Scale (FARS) is made up of a measure of ataxia, an activities of daily living subscale and a neurological subscale. This scale also includes the 8m walk at maximum speed (8MW), the 9-hole peg test (9HPT), and low-contrast letter acuity.
 
Strengths: FARS scores correlate significantly with functional disability, activities of daily living scores and disease duration. FARS has a large effect size and requires fewer patients for an equivalently powered study.
 
Weaknesses: This scale captures a particular dimension of neurologic function in FA, so as a composite measure, it is not good enough to predict disease status.

Scoring:	
The scores from the three subscales are added to generate a total score ranging from 0 to 159, with a higher score indicating a greater level of disability.
 
Functional Staging for Ataxia subscale scoring: 0 = Normal - 6.0 = Confined to wheelchair or bed with total dependency for all ADL. Total disability.
 
ADL subscale scoring: 9 items scored from 0 to 4.
 
Neurological Examination subscale scoring: 5 items scored from 0 to 2 or 0 to 5, depending on the specific parameter.

References:	
Key Reference:
 
 
Other References:
 
Delatycki MB. Evaluating the progression of Friedreich ataxia and its treatment. J Neurol. 2009. 256(Suppl 1):36-41.
 
 
 
Subramony SH, May W, Lynch D, Gomez C, Fischbeck K et al. Measuring

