TOTAL ACTIVITIES OF DAILY LIVING SCORE:

III. NEUROLOGICAL EXAMINATION (rate each item on the basis of the patient status during examination. To the extent possible, sequential patient examinations should be carried out at the same time of the day. If the patient is taking any medication, the examination should be carried out prior to dosing, or at a fixed time following the dosing based on the maximum expected therapeutic response. Increments of 0.5 may be used if examiner feels an item falls between 2 defined severities)

A. BULBAR

1. Facial Atrophy, Fasciculation, Action Myoclonus, and Weakness:
0 - None
1 - Fasciculations or action myoclonus, but no atrophy.
2 - Atrophy present but not profound or complete.
3 - Profound atrophy and weakness.

2. Tongue Atrophy, Fasciculation, Action Myoclonus and Weakness:
0 - None.
1 - Fasciculations or action myoclonus, but no atrophy.
2 - Atrophy present but not profound or complete.
3 - Profound atrophy and weakness.

3. Cough: (Patient asked to cough forcefully 3 times)
0 - Normal.
1 - Depressed.
2 - Totally or nearly absent.

4. Spontaneous Speech (ask the patient to read or repeat the sentences "The President lives in the White House" or "The traffic is heavy today":
0 - Normal.
1 - Mild (all or most words understandable).
2 - Moderate (most words not understandable).
3 - Severe (no or almost no useful speech).

TOTAL BULBAR SCORE:

B. UPPER LIMB COORDINATION

1. Finger to Finger Test (The index fingers are placed in front of each other with flexion at the elbow about 25 cm. from the sternum. Observe for 10 seconds. Score amplitude of oscillations):
0 - Normal.
1 - Mild oscillations of finger (< 2 cm.).
2 - Moderate oscillations of finger (2-6 cm.).
3 - Severe oscillations of finger (> 6 cm.).

Right Left

2. Nose-Finger Test (Assess kinetic or intention tremor during and towards the end of movement: examiner holds index finger at 90% reach of patient; test at least 3 nose-finger-nose trials; movement slow > 3 sec.):

- 0 - None
- 1 - Mild (< 2 cm. amplitude).
- 2 - Moderate (2-4 cm. amplitude or persisting through movement).
- 3 - Severe (> 6 cm. & persisting through movement).
- 4 - Too poorly coordinated to perform task.

Right	Left
	

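### The week-12 neurological definition in Section 3.1 places a subject with a clear FARS fall but no faster walk in both classes, and this class helps to set the dose for weeks 12 to 24.

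*Combined protocol and SAP*

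**What the plan says.** Section 3.1 (General Design) contains two neurological definitions.

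- *No improvement/worsening* has two arms, and either is enough. The walk arm reads "If there is no change or the timed walk is longer at 12 weeks than at the baseline walk time". The other arm is a FARS composite that stays the same or rises.
- *Improvement*: "Improvement is defined as a greater than 1 point decrease in the FARS composite score, as compared to the baseline composite score". Walk time does not appear.

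The same section keeps improvers at 75 mg/day and escalates the others to 150 mg/day until week 24. Its escalation sentence is triggered by failure to improve in either the neurological or the cardiac domain.

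Section 3, Visit 2, refers back to the Section 3.1 definition but keeps the dose if there is improvement "compared to baseline in composite score, including the 8m timed walk or cardiac function by MRI". There the walk is part of the composite, and improvement in either domain is enough to stay. Footnote g of Attachment II names the timed walk as the only neurological criterion and does not mention the FARS score.

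On the instrument, Attachment I says "The scores from the three subscales are added to generate a total score ranging from 0 to 159". In the neurological examination, "Increments of 0.5 may be used if examiner feels an item falls between 2 defined severities". Half steps are also allowed in the functional staging and the daily-living items.

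**The concern.** A rule that assigns dose should give every possible pair of FARS and walk results exactly one class. Here the two classes are written independently, one using two measures and the other using one, and neither is the complement of the other. Discordant results are plausible: a subject may score better on the examination while walking no faster.

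What is at stake is exposure in weeks 12 to 24, which is half of the treatment period. Change in FARS at 24 weeks is a primary endpoint (Section 3.2), and the trial is open label (Section 5.7). The person applying the rule knows the results and the treatment, and for some subjects could defend either class from identical measurements. The mix of doses behind the week-24 results would then depend partly on how the rule is read.

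**Working it through.** **Step 1. Classes.** Let F be the change in FARS composite and W the change in walk time, week 12 minus baseline. From Section 3.1:

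- No improvement/worsening: W ≥ 0 or F ≥ 0.
- Improvement: F < −1.

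| FARS change | Walk shorter | Walk unchanged or longer |
|---|---|---|
| F < −1 (e.g. −1.5, −2) | Improvement only | **Both** |
| −1 ≤ F < 0 (−0.5, −1.0) | **Neither** | No improvement only |
| F ≥ 0 | No improvement only | No improvement only |

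Two of the six cells fail. Both can occur. The gap does not even need half-point scoring, because a fall of exactly 1 is not greater than 1.

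**Step 2. Does another passage settle it?** No passage gives precedence between walk and score. The walk is a separate trigger in Section 3.1, a component of the composite in Visit 2, and the sole neurological criterion in footnote g. The 0–159 total in Attachment I adds functional staging, daily living and neurological examination, and has no term for seconds walked.

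**Step 3. Does the cardiac result settle the dose?** First take subjects whose two classes are clear:

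| Neurological | Cardiac | Section 3.1 escalation sentence | Visit 2 |
|---|---|---|---|
| Improved | Improved | Stay | Stay |
| Improved | Not improved | Escalate | Stay |
| Not improved | Improved | Escalate | Stay |
| Not improved | Not improved | Escalate | Escalate |

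The two texts conflict whenever exactly one domain improves. Under the Section 3.1 sentence the neurological class decides only when the heart improved. Under Visit 2 it decides only when the heart did not. Read together, the cardiac result does not reliably settle the dose of a subject in a *both* or *neither* cell.

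**Step 4. How often?** The documents give no variability for either measure, so every input here is an assumption: F normal with SD 3 to 6 and mean drift 0 to +1 point, recorded to 0.5; walk change symmetric about zero; correlation between F and W from 0 to 0.8.

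With no drift and correlation 0, the shares can be worked by hand. A recorded fall of more than 1 point means an underlying value below −1.25, and a recorded fall of 0.5 or 1.0 means one between −1.25 and −0.25. Each walk direction has probability 0.5.

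- SD 6, both: 0.5 × Φ(−1.25/6) = 0.5 × 0.4175 = 20.9%.
- SD 6, neither: 0.5 × [Φ(−0.25/6) − Φ(−1.25/6)] = 0.5 × (0.4834 − 0.4175) = 3.3%.
- Sum: 24.2%.

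For correlated measures the same two events were simulated, with 2 million draws per setting:

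- No drift, correlation 0 to 0.6: both 7.7% to 20.9%, neither 3.3% to 7.4%, total 14.4% to 24.2%.
- Allowing drift of +1 point and correlation up to 0.8: the lowest total is 8.5% (SD 6, drift +1, correlation 0.8), so the full range is about 8% to 24%.

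In a trial of 10 this is about 0.8 to 2.4 subjects.

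**The case against.** **The gap is a hyper-literal reading.** Visit 2 is binary: improvement as defined in Section 3.1 keeps the dose, and otherwise it rises. A fall of 0.5 or 1.0 point is not defined improvement, so the ordinary reading is no improvement. This largely stands, and it is why the gap is secondary. It is not conclusive, because Section 3.1 expressly defines its no-improvement FARS arm as unchanged or increased. It does nothing for the overlap.

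**The instrument does include a walk.** Attachment I describes an 8 m walk at maximum speed as part of the scale, and its gait item times an 8 m walk out and back at normal pace. This gives Visit 2 some basis. However, the gait item is graded on ataxia and support, so seconds do not enter the total, and Section 3.1 still uses the walk as a separate trigger.

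**The neurological class is only one of two determinants of dose.** This stands. A reader might infer that the class alone fixes the dose, or that the frequencies above are shares of subjects with an indeterminate dose. The documents support neither, because cardiac MRI also counts and for some subjects makes the neurological class irrelevant under one or other text.

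**It is not the only improvement criterion, and no analysis uses it directly.** This also stands. The interim analysis in Section 7.2 has its own FARS criterion at 3 months, an improvement of more than 30%. FARS is analysed as a continuous change from baseline by paired t-test or Wilcoxon test. A reader might infer that a responder count is compromised, but no neurological responder endpoint is planned. The effect on the analysis runs through second-half exposure.

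**Conclusion.** The definition is wrong as written, not merely thin. A FARS composite fall of more than 1 point with an unchanged or longer walk satisfies two opposite labels in a rule that contributes to dose, and no passage resolves it. This follows from the text alone and needs no assumption. The gap for small falls with a shorter walk is real on a literal reading but can be read away. The three roles given to the walk, and the opposite handling of subjects who improve in exactly one domain, mean that neither Visit 2 nor footnote g can be used to repair Section 3.1.

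The size is uncertain. About 8% to 24% of subjects with an indeterminate neurological class is an illustration resting on the assumed SD, drift and correlation, none of which comes from the documents. It counts classes, not doses. All other combinations of walk and score are classified uniquely.

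**What to change.** Reconcile Section 3.1, Visit 2 and footnote g into one definition and repeat it in identical words:

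1. Define *improvement* once, and make *no improvement/worsening* its exact complement, so that discordant results and falls of 0.5 or 1.0 point each have one class.
2. State what *composite score* means, and whether walk time is inside it, a separate condition, or not used. If the walk is used, say which one (maximum speed or normal pace).
3. State how the neurological and cardiac results combine when only one has improved.

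Which measure governs, and which dose follows, is for the investigator to decide; the point is only that the passages must agree. The cost is one paragraph of protocol text with matching wording in Visit 2 and footnote g. It needs no new data, visits or subjects.

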Improvement in left ventricular structure and function by MRI is defined as any one of the following:

1. If LV mass was abnormally increased at baseline, reduction in LV mass of > 10% from baseline or
2. If LV ejection fraction was reduced at baseline, increase in LV ejection fraction of > 5% from baseline or
3. If LV end-diastolic volume was abnormally increased at baseline, reduction in LV end-diastolic volume of > 10% from baseline.

Neurologic Status: If spinal cord and cerebellar volumes (based on 3D volumetric MRI), fractional anisotropy (based on DTI), and metabolites (based on 3D MRS) are worse at 24 weeks compared to baseline, this will be considered no improvement /worsening of neurologic structure/function.

Worsening in neurologic structure and function by MRI is defined as any one of the following:

1. If spinal cord volumes were abnormally decreased at 24 weeks compared to baseline, reduction in cord volume of > 10% from baseline or
2. If cerebellar volumes were abnormally decreased at 24 weeks compared to baseline, reduction in cerebellar volume of > 10% from baseline or
3. If spinal cord fractional anisotropy was abnormally decreased at 24 weeks compared to baseline, reduction in fractional anisotropy of > 10% from baseline or
4. If cerebellar metabolite ratios (NAA/Cr, Cho/Cr, NAA/Cho) change > 5% from baseline at 24 weeks.

Study drug will be dispensed at the baseline visit for 12 (+2) weeks of dosing initially and resupplied at the 12 week visit for an additional 12 (+2) weeks of dosing at either the starting dose or escalated dose following re-assessment for changes in neurological and cardiac functions as described above.

Table 1

Neuromuscular	Cardiac	Metabolic & Biochemical
FARS (disability, ataxia, fine motor skills, peripheral neuropathy, and gait)	MRI (left ventricular mass, end-diastolic and end-systolic volumes, ejection fraction, strain analysis, myocardial fibrosis)	Glucose tolerance test
Brain MRI (spinal cord and cerebellar volumetry, DTI, and MRS)	Blood Oxygenation Level Dependent (BOLD) MRI (myocardial oxygenation)	Whole Blood Hemoglobin A1C Frataxin

		Heart Failure Biomarkers (BNP, and others) triglycerides
Magnetic Resonance Spectroscopy (lactate, N-acetylaspartate, and choline)	Regadenoson-stress-perfusion MRI (myocardial perfusion index)	Leukocytes ETC Complexes Other relevant proteins Bioenergetics

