4.1 Inclusion Criteria

Subjects must fulfill all of the following criteria:

Inclusion criteria:

- Confirmed diagnosis of Friedreich's ataxia by *FXN* genetic testing and/or Frataxin enzyme analysis
- Between age 10 and 50 years of age, inclusive
- Body weight of 25 kg or higher
- Minimum of one affected organ (cardiac or neurological) system, as evidenced by clinical signs/symptoms
- Disease duration ≤ 7 years, based on onset date of FA symptoms
- Has no known contraindication to gadolinium contrast such as severe allergy or GFR < 30 ml/min/m².
- Has no known contraindication to non-contrast MRI evaluation such as pacemaker or magnetically active metal fragments.
- Women of childbearing age must:
 - Have a negative pregnancy human chorionic gonadotropin test prior to receiving study drug.
 - Agree to use contraception for the duration of the study drug dosing, plus 1 month after completion of the study.

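### The week-12 cardiac criteria have no class for a subject with normal LV values and no rule for discordant LV measures, and the conflicting dose rules then treat the same subject differently

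*Combined protocol and SAP*

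**What the plan says.** All references are to the combined protocol and SAP.

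**Definition (Section 3.1).** "Improvement in left ventricular structure and function by MRI is defined as any one of the following". The items are:

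- LV mass: "If LV mass was abnormally increased at baseline, reduction in LV mass of > 10% from baseline or"
- Ejection fraction (EF): "If LV ejection fraction was reduced at baseline, increase in LV ejection fraction of > 5% from baseline or"
- End-diastolic volume (EDV): "If LV end-diastolic volume was abnormally increased at baseline, reduction in LV end-diastolic volume of > 10% from baseline"

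Just before the list stands a companion sentence: "If the cardiac function is the same as baseline or worse at 12 weeks, this will be considered no improvement /worsening of cardiac LV structure/function".

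**Eligibility (Section 4.1).** One affected system is enough: "Minimum of one affected organ (cardiac or neurological) system, as evidenced by clinical signs/symptoms".

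**Dose rule, in three places.**

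- The escalation paragraph of Section 3.1 raises the dose for subjects who fail neurologically "or with no improvement in cardiac function by MRI at the 12-week clinical assessment".
- Footnote g of Attachment II likewise raises it when either the timed walk or the cardiac evaluation fails to improve.
- The Visit 2 text in Section 3 keeps the dose if the subject improves on the composite score (including the timed walk) or on cardiac MRI. It takes its meaning of improvement from Section 3.1.

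**The concern.** The classification is applied to every subject at week 12 and helps to set the dose for the remaining 12 weeks. Two kinds of subject expose gaps in it.

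The first has normal LV mass, EF and EDV at baseline. No item in the list can apply, and no class says that the cardiac domain is uninformative. The companion sentence puts an unchanged normal heart with the failures. Under the escalation paragraph and footnote g, only subjects with at least one abnormal LV value at baseline could stay at the starting dose. Dose in weeks 12 to 24 would then partly reflect baseline cardiac status rather than response. Section 7.2 analyses week-24 outcomes as paired changes; it mentions covariate adjustment but does not name dose.

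The second has LV measures that move in opposite directions. Two assessors who both follow Section 3.1 could reach opposite classes. With 10 subjects, each one is 1/10 = 10% of the sample.

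**Working it through.** The plan states no figure for this point. The check is logical, with small arithmetic illustrations.

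**1. Normal baseline.** Each item has the form (measure abnormal at baseline) AND (change beyond threshold), and the items are joined by OR. With three normal values every first condition is false, so every item is false whatever week 12 shows. As confirmation, a grid of 38,584 outcomes from one illustrative normal baseline, covering both readings of the EF threshold, produced 0 that met any item.

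**2. Dose consequence.** Take *neurologically improved* to mean improved on both the timed walk and the FARS composite, so that the neurological definitions agree.

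| Neurological | Cardiac | Section 3.1 escalation paragraph; footnote g | Section 3, Visit 2 |
|---|---|---|---|
| not improved | not improved | raise | raise |
| not improved | improved | raise | keep |
| improved | not improved | raise | keep |
| improved | improved | keep | keep |

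The texts disagree in the two middle rows. A subject with normal LV values can only be in row 1 or row 3. In row 3 the dose is raised under two texts and kept under the third. Under the escalation paragraph and footnote g that subject is escalated in both rows, so the week-12 cardiac MRI carries no response information for the decision.

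**3. Discordant measures (illustrative values, not from the documents).**

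- LV mass abnormally high at 200, falling to 176: (176 − 200)/200 = −12%, so the mass item is met. EF falls from 60% to 45%.
- EDV abnormally high at 200, falling to 176 (−12%), with end-systolic volume fixed at 100. The EDV item is met. EF goes from (200 − 100)/200 = 50% to (176 − 100)/176 = 43.2%.

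By the any-one-of list both subjects are improved. By the companion sentence both can be read as worse. From the table, the choice of class changes the dose under the escalation paragraph and footnote g when the subject is neurologically improved (row 3 against row 4). Under Visit 2 it changes the dose when the subject is not (row 1 against row 2).

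**4. EF unit.** For baseline EF b, the relative reading requires more than 1.05 × b and the points reading more than b + 5. At b = 40% these are 1.05 × 40 = 42% and 40 + 5 = 45%. A week-12 EF of 44% is +10% relative (44/40 = 1.10) but +4 points, so it is improved on one reading and not on the other.

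**The case against.** The strongest reply is that the list affects only the week-12 dose decision. That is correct, and it rules out several stronger readings that a reader might infer.

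- *A cardiac responder rate would be capped or biased.* None is planned. The cardiac endpoints in Section 3.2 are changes from baseline, Section 7.2 tests continuous endpoints with a paired t-test or Wilcoxon test, and the interim criterion there uses a separate 30% threshold. The documents also do not say how many subjects would have three normal values. Section 4.1 goes by clinical signs and symptoms and Section 3.1 by MRI values, so a subject enrolled on neurological signs may still have an abnormal LV value.
- *A falling EF would be recorded as benefit.* EF is itself a primary measure in Section 3.2, so a fall enters the endpoint analysis as a fall.
- *A subject with normal LV values is always escalated.* Visit 2 says otherwise when the neurological measures improve.
- *The classification is clinically wrong.* For an unchanged normal heart, no improvement is literally true. Whether it should count towards escalation is a clinical judgement that the documents do not settle.

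Two narrower replies carry some weight. The companion sentence might be meant only as the remainder of the list, in which case discordant subjects are improved; but the text does not say so. The three items share one form, which favours a relative reading for EF; but EF is already a percentage, so the unit should be stated.

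None of this removes the missing class or the conflict between the dose rules.

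**Conclusion.** The point holds as a defect in a stated rule, and it is more than missing detail. An eligible subject with normal LV mass, EF and EDV can never be classed as cardiac improved. If neurologically improved, that subject is escalated under the Section 3.1 escalation paragraph and footnote g but stays at the starting dose under Visit 2. Subjects with discordant LV measures can be given opposite classes from adjacent statements in Section 3.1. The EF threshold differs by 45 − 42 = 3 points at a baseline of 40%, depending on the unit.

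The conclusion rests on a literal reading of the dose texts and on at least one such subject being enrolled, which eligibility allows but does not guarantee. How often these cases would arise cannot be sized from the documents. The harm lies in the reproducibility of the dose classification, not in a planned cardiac responder analysis.

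**What to change.** Make one wording amendment before the week-12 rule is applied:

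1. Reconcile the Visit 2 text, the escalation paragraph and cardiac definition in Section 3.1, and footnote g of Attachment II into a single rule, stated once and cross-referenced elsewhere.
2. Add a class, not evaluable for cardiac improvement, for subjects with no abnormal LV value at baseline, and state how the week-12 decision is made for them. The documents give no limits for calling a baseline value abnormal; this class needs them.
3. Give a subject with one LV measure improving and another deteriorating a single class, by saying whether the list or the companion sentence takes precedence.
4. State whether the EF change is in percentage points or relative to baseline.

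The clinical content of each choice is the sponsor's. The cost is an amendment to the wording, with no added scan, visit or subject.
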